### **Individual Concentration vs. Time Profiles**

- Individual concentrations will be plotted utilizing actual sampling times.
- The terminal point selections will be indicated on a semi-logarithmic plot.
- Observed (unadjusted) concentrations will be plotted for C10 and SNAC.

### **Average Concentration vs. Time Profiles**

- The average concentration profiles will be graphed using scheduled (nominal) sampling times.
- The average concentration profiles will be graphed using arithmetic average concentrations.
- The pre-dose average concentration for single-dose data from non-endogenous compounds will be set to zero. Otherwise, only quantifiable concentrations will be used to calculate average concentrations.
- Concentrations at a sampling time exceeding the sampling time window specified in the protocol, or  $\pm 10\%$ , will be excluded from the average concentration profiles.
- Concentrations excluded from the mean calculation will be documented in the final study report.
- A concentration average will be plotted for a given sampling time only if 2/3 of the individual data at the time point have quantifiable measurements that are within the sampling time window specified in the protocol or  $\pm 10\%$ . An average concentration estimated with less than 2/3 but more than 3 data points may be displayed on the mean concentration plot if determined to be appropriate and will be documented within the final study report.

- Observed (unadjusted) concentrations will be plotted for C10 and SNAC.

### **Treatment of Outliers during Pharmacokinetic Analysis**

Application of this procedure to all pharmacokinetic analyses is not a requirement. Rather, this procedure provides justification for exclusion of data when scientifically appropriate. This procedure describes the methodology for identifying an individual value as an outlier for potential exclusion, but does not require that the value be excluded from analysis. The following methodology will not be used to exclude complete profiles from analysis.

#### Data within an Individual Profile

A value within an individual profile may be excluded from analysis if any of the following criteria are met:

- For pharmacokinetic profiles during multiple dosing, the concentration of the pre-dose sample exceeds all measured concentrations for that individual in the subsequent post-dose samples.
- For pharmacokinetic profiles during single dosing of non-endogenous compounds, the concentration in a pre-dose sample is quantifiable.
- For any questionable datum that does not satisfy the above criteria, the profile will be evaluated and results reported with and without the suspected datum.

#### Data between Individual Profiles

1. If  $n < 6$ , then the dataset is too small to conduct a reliable range test. Data will be analyzed with and without the atypical value, and both sets of results will be reported.
2. If  $n \geq 6$ , then an objective outlier test will be used to compare the atypical value to other values included in that calculation:
  - a. Transform all values in the calculation to the logarithmic domain.
  - b. Find the most extreme value from the arithmetic mean of the log transformed values and exclude that value from the dataset.
  - c. Calculate the lower and upper bounds of the range defined by the arithmetic mean  $\pm 3*SD$  of the remaining log-transformed values.
  - d. If the extreme value is within the range of arithmetic mean  $\pm 3*SD$ , then it is not an outlier and will be retained in the dataset.
  - e. If the extreme value is outside the range of arithmetic mean  $\pm 3*SD$ , then it is an outlier and will be excluded from analysis.

If the remaining dataset contains another atypical datum suspected to be an outlier and  $n \geq 6$  following the exclusion, then repeat step 2 above. This evaluation may be repeated as many times as necessary, excluding only one suspected outlier in each iteration, until all data remaining in the dataset fall within the range of arithmetic mean  $\pm 3*SD$  of the log-transformed values.

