## **6. BLINDING**

This is a randomized, open-label study.

The Fortrea biometrics and Eli Lilly study teams will be unblinded throughout the study.

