### Reporting of Excluded Values

Individual values excluded as outliers will be documented in the final report. Approval of the final report will connote approval of the exclusion.

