### **10.3.2 Pharmacokinetic Statistical Methodology**

The PK parameters of LY3493269 will be evaluated to estimate the relative bioavailability. Log-transformed  $AUC_{\tau}$ ,  $AUC(0-t_{last})$ ,  $AUC(0-\infty)$  (profile day 3 only) and  $C_{max}$  of LY3493269 will be evaluated in a mixed model for repeated measures with fixed effects for treatment, profile day and the treatment-by-day interaction, and a random effect for participant. An unstructured covariance structure will be used to model the covariance between a participant's multiple observations, with an alternative structure to be used if the model fails to converge. The geometric least squares means, ratio of geometric least squares means and corresponding 90% CI will be reported.

One model including all treatments (A1, A2, A3, B1 and B2) will be used to present the following comparisons for each profile day:

- Test capsule X versus Reference tablet, where X=1, 2 or 3.
- Fed versus fasted, for matching formulation.
- 240 mL versus 120 mL water administration, for matching formulation and dietary status.

Example SAS code:

```
proc mixed data=xxxx;
  by param;
  class treat day subjid;
  model lpk = treat day treat*day / residual ddfm=kr2;
  repeated day / subject=subjid type=un;
  lsmeans treat*day / cl pdiff alpha=0.1;
  ods output lsmeans=lsm diff=dif;
run;
```

The parameter  $t_{max}$  of LY3493269 will be analyzed non-parametrically. Estimates of the median difference, approximate 90% CI and p-value from the Wilcoxon rank sum test will be calculated.

All PK parameters will be summarized using descriptive statistics.

Additional analysis may be conducted if deemed necessary.

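### The SAP's 3 SD outlier rule, if applied routinely, drops a valid value in about 22% of clean groups of 10 and cuts 90% CI coverage to about 85%, with no full-data result required

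*SAP*

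**What the plan says.** The rule is in SAP 10.3.1, Treatment of Outliers during Pharmacokinetic Analysis.

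- **Status of the procedure.** The introduction says it need not be applied to every PK analysis. It identifies candidates for exclusion "but does not require that the value be excluded from analysis".
- **Fewer than 6 values** (Data between Individual Profiles, item 1). "Data will be analyzed with and without the atypical value, and both sets of results will be reported".
- **Six or more values** (item 2). On the log scale, step 2b reads: "Find the most extreme value from the arithmetic mean of the log transformed values and exclude that value from the dataset". Step 2c sets limits at mean ± 3 SD of the remaining values. Step 2e says that a value outside them is removed: "then it is an outlier and will be excluded from analysis". The test may be repeated while at least 6 values remain.
- **Reporting.** "Individual values excluded as outliers will be documented in the final report". Approval of the report counts as approval of the exclusion.
- **Model.** SAP 10.3.2 fits log AUC and Cmax by treatment and profile day: "The geometric least squares means, ratio of geometric least squares means and corresponding 90% CI will be reported". It does not say whether excluded values leave the data set.
- **Blinding** (SAP 6). "The Fortrea biometrics and Eli Lilly study teams will be unblinded throughout the study".

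The target is 10 completers per treatment (SAP 5). With Part B cancelled (SAP 12), three groups remain.

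**The concern.** There are three linked problems.

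1. **The limit is crossed too easily at this sample size.** The tested value is chosen because it is the furthest out, and it is compared with a mean and SD estimated from the other nine values after it has been taken away. Three SDs sounds strict, but under those conditions it is not.
2. **Step 2e and the introduction disagree.** One says a flagged value goes; the other says it need not. The introduction's only criterion is scientific appropriateness, and those deciding know the treatment assignments.
3. **Disclosure is weakest at the planned group size.** Below 6 values the reader gets both results. At 10 the reader gets a list of excluded values but need not be shown the ratio with them included.

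At stake are the 90% CIs for the primary comparison. Trimming valid tails shrinks the estimated SD, so the intervals are too short for their label. Protocol 4.2 expects very high between- and within-person variability in oral bioavailability, so an extreme value may well be genuine behaviour of the formulation.

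**Working it through.** The documents give no false-exclusion rate or coverage for this rule, so there is no planned figure to reproduce.

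**Inputs.** Group size 10, three groups, 3 SD limits from the remaining n − 1 values, iteration while n ≥ 6, and a 90% CI (all from the SAP). Clean data are taken as normal on the log scale, since SAP 10.1 treats AUC and Cmax as log-normal. The log SD is not needed, because the flag rate and coverage do not depend on it.

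**Step 1: flag rate, first pass.** For normal data, (value − mean of the rest) / (SD of the rest × √(1 + 1/(n − 1))) follows t with n − 2 df. Any of the n values could be the one flagged, so

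P(at least one flag) ≈ n × P(|t(n−2)| > 3/√(1 + 1/(n − 1))).

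| n | Limit on t scale | df | Two-sided P | n × P | Simulated |
|---|---|---|---|---|---|
| 6 | 2.739 | 4 | 0.0520 | 31.2% | 31.1% |
| 8 | 2.806 | 6 | 0.0309 | 24.7% | 24.8% |
| 10 | 2.846 | 8 | 0.0216 | 21.6% | 21.6% |
| 12 | 2.872 | 10 | 0.0166 | 19.9% | 19.8% |

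The simulation applies the full iterated step 2 to 40,000 groups per n. With a known mean and SD, a 3 SD limit would flag a value in 1 − (1 − 0.0027)^10 = 2.7% of groups of 10. That is a benchmark for how 3 SD is usually understood, not an available alternative.

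At n = 10, about 5% of groups lose two or more values, and the group SD falls by 8.5% on average over all groups. Across three groups, the chance that at least one value is lost for a given parameter and day is 1 − (1 − 0.216)³ = 52%.

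**Step 2: coverage, one day.** Three arms of 10, pooled-variance t interval for test minus reference, 30,000 trials, rule applied to every arm:

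- All data kept: coverage 90.1%.
- Rule applied: coverage 85.2%, mean width 0.948 of the full-data interval. Repeat simulations gave 85.4–85.6%.
- Mean shift in the log difference: −0.0006 SD, so no bias on average.
- In the roughly 38% of trials where one of the two compared arms lost a value, coverage was about 79%, against 90% with all data.

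**Step 3: coverage, three-day model.** REML with an unstructured 3 × 3 covariance and arm-by-day means, as in SAP 10.3.2, with approximate df in place of the SAP's Kenward-Roger option. Day 3 contrast, 4,000 trials per setting (Monte Carlo SE about 0.6 points). The between-day correlations are assumptions; the documents give none.

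| Correlation | All data | Rule applied | Width ratio |
|---|---|---|---|
| 0.3 | 90.1% | 85.2% | 0.946 |
| 0.7 | 89.6% | 86.2% | 0.951 |

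**Step 4: partial use.** With the rule applied to a random half of groups, coverage is 87.4% (88.0% on repetition). Applied to a random quarter, it is 88.9% (88.7% on repetition). Random use does not represent a choice made after seeing the results, which was not modelled.

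**The case against.** The strongest reply is that the SAP does not tell anyone to run this test on every arm, day and parameter. The procedure is optional and aimed at a value already thought atypical, so 22% and 85% describe a scenario the SAP does not prescribe. That stands as a limit on the figures: they are the full-application case, and selective use falls between them and nominal. It does not remove the problem, because discretion replaces a known error rate with an unspecified choice by unblinded staff.

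Second, the rule sits in the noncompartmental section, the modelling section never refers to it, and the SAP bars using it to exclude complete profiles. Exclusion might therefore affect only summary statistics or mean profiles. This is a fair reading, and the coverage loss depends on the other one. But step 2e puts no limit on which analysis it means, and the bar on complete profiles does not clearly protect a single AUC or Cmax.

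Third, the consequence may be modest. With an assumed CV of 50%, the log SD is √ln(1.25) = 0.472 and the 90% half-width is 1.703 × 0.472 × √(2/10) = 0.360. The CI factor is then e^0.360 = 1.43, falling to e^(0.95 × 0.360) = 1.41 under the rule. At a CV of 100% it goes from 1.89 to 1.83. No equivalence margin or decision rule is stated, and Part B is cancelled. All of that is true. Even so, non-coverage rises from 10% to about 15%, in the intervals on which the primary comparison rests.

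Fourth, exclusions are documented, listings cover all data, and a questionable point within one profile that meets neither listed criterion already gets both results. This helps a reader rebuild the full-data ratio but does not oblige the report to show it.

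**Conclusion.** The concern holds and should be fixed. The two statements on exclusion conflict, and at the planned group size no full-data result is required. Applied to every group with every flag acted on, the rule removes at least one valid value from about 22% of clean groups of 10. If exclusions reach the SAP 10.3.2 model, the nominal 90% intervals cover about 85–86% and are about 5% too narrow.

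These figures rest on log-normal clean data, routine application, and carry-over into the model. The flag rate follows from a standard t result and is firm. The coverage loss is equally reproducible given carry-over, but the SAP leaves carry-over unstated. The fault lies in interval coverage and the open choice, not in the average ratio.

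**What to change.** - In SAP 10.3.2, state that the primary model uses all values unless a dosing, sampling or assay error is documented.
- In Data between Individual Profiles, make step 2 a flagging test only, and reword step 2e to agree with the introduction to the procedure.
- Require results with and without flagged values at every group size, extending what the SAP already does below 6.
- Say what counts as a value (a concentration, a parameter, or both) and which data set feeds the model and which the summary tables.

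The cost is SAP wording and one sensitivity table. The primary intervals will be about 5% wider than under full application of the rule (1/0.948 = 1.05), which is the width needed for the stated 90% coverage.

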### Reporting of Excluded Values

Individual values excluded as outliers will be documented in the final report. Approval of the final report will connote approval of the exclusion.

### **10.3.2 Pharmacokinetic Statistical Methodology**

The PK parameters of LY3493269 will be evaluated to estimate the relative bioavailability. Log-transformed  $AUC_{\tau}$ ,  $AUC(0-t_{last})$ ,  $AUC(0-\infty)$  (profile day 3 only) and  $C_{max}$  of LY3493269 will be evaluated in a mixed model for repeated measures with fixed effects for treatment, profile day and the treatment-by-day interaction, and a random effect for participant. An unstructured covariance structure will be used to model the covariance between a participant's multiple observations, with an alternative structure to be used if the model fails to converge. The geometric least squares means, ratio of geometric least squares means and corresponding 90% CI will be reported.

One model including all treatments (A1, A2, A3, B1 and B2) will be used to present the following comparisons for each profile day:

- Test capsule X versus Reference tablet, where X=1, 2 or 3.
- Fed versus fasted, for matching formulation.
- 240 mL versus 120 mL water administration, for matching formulation and dietary status.

Example SAS code:

```
proc mixed data=xxxx;
  by param;
  class treat day subjid;
  model lpk = treat day treat*day / residual ddfm=kr2;
  repeated day / subject=subjid type=un;
  lsmeans treat*day / cl pdiff alpha=0.1;
  ods output lsmeans=lsm diff=dif;
run;
```

The parameter  $t_{max}$  of LY3493269 will be analyzed non-parametrically. Estimates of the median difference, approximate 90% CI and p-value from the Wilcoxon rank sum test will be calculated.

All PK parameters will be summarized using descriptive statistics.

Additional analysis may be conducted if deemed necessary.

### **10.4 Safety and Tolerability Assessments**

#### **10.4.1 Adverse events**

Where changes in severity are recorded in the Case Report Form (CRF), each separate severity of the adverse event (AE) will be reported in the listings, only the most severe will be used in the summary tables. A pre-existing condition is defined as a condition that starts before the participant has provided written informed consent and is ongoing at consent. A non-treatment emergent AE is defined as an AE which starts after informed consent but prior to the first dose.

A treatment-emergent AE is defined as an AE which occurs postdose or which is present prior to dosing and becomes more severe postdose.

All AEs will be listed. TEAEs will be summarized by treatment, severity and relationship to the study drug. The frequency (the number of AEs, the number of participants experiencing an AE and the percentage of participants experiencing an AE) of TEAEs will be summarized by treatment, Medical Dictionary for Regulatory Activities (MedDRA) (version is documented in the Data Management Plan [DMP]) system organ class and preferred term. The summary and frequency AE tables will be presented for all causalities and those considered related to the study drug by the investigator. Any serious AEs will be listed. AEs by day of onset will be presented.

Discontinuations due to AEs will be listed.

Adverse events of special interest (AESI) are nausea, vomiting, diarrhea, skin burning sensations and related AEs. AESIs will be listed.

#### **10.4.2 Skin Burning Sensations and Related AEs**

Healthy participants in this short-exposure study may experience AEs of skin burning sensation and related AEs. If this AE does occur, dedicated CRF will be used by site personnel to collect detailed information about the event on initial presentation of this AE, and on subsequent visits until the AE resolves.

The data will be summarized by treatment and listed.

#### **10.4.3 Glucose Monitoring and Hypoglycemia**

During the study, plasma glucose concentrations will be monitored for safety assessments. Glucose data will be listed and summarized by treatment together with changes from baseline, where baseline is defined as Day 1 pre-breakfast.

Hypoglycemic events will be appropriately recorded in the CRF. In the case of a hypoglycemic event, the actual blood glucose value, if measured, will be recorded in the CRF, together with any treatments administered. Each category of hypoglycemic events (defined below) will be listed and summarized by treatment. Hypoglycemia is defined as follows:

- **Level 1 hypoglycemia:**

**Glucose <70 mg/dL (3.9 mmol/L) and  $\geq$  54 mg/dL (3.0 mmol/L):** Level 1 hypoglycemia can alert a person to take action such as treatment with fast-acting carbohydrates. Providers should continue to counsel participants to treat hypoglycemia at this glucose alert value.

- **Level 2 hypoglycemia:**

**Glucose <54 mg/dL (3.0 mmol/L):** This is also referred to as documented or blood glucose confirmed hypoglycemia with glucose <54 mg/dL (3.0 mmol/L). This glucose threshold is clinically relevant regardless of the presence or absence of symptoms of hypoglycemia.

- **Level 3 hypoglycemia:**

**Severe hypoglycemia (in adults):** A severe event characterized by altered mental and/or physical status requiring assistance for treatment of hypoglycemia. For example, participants had altered mental status, and could not assist in their own care, or were semiconscious or unconscious, or experienced coma with or without seizures, and the assistance of another person was needed to actively administer carbohydrate, glucagon, or other resuscitative actions. Glucose measurements may not be available during such an event, but neurological recovery attributable to the restoration of glucose concentration to normal is considered sufficient evidence that the event was induced by a low glucose concentration.

- The determination of a hypoglycemic event as an episode of severe hypoglycemia, as defined above, is made by the investigator based on the medical need of the participant to have required assistance and is not predicated on the report of a participant simply having received assistance.

- **Other hypoglycemia categories:**

- **Nocturnal** hypoglycemia is defined as a hypoglycemia event (including severe hypoglycemia) that **occurs at night** and presumably during sleep.

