**Data Monitoring Committee: No**

## 1.2. Schema

**Figure GZHI.1.1      Illustration of Parts A and B for Protocol J1X-MC-GZHI.**

### 1.3. Schedule of Activities (SoA)

#### Schedule of activities for Parts A and B

Study Activities	Screen	Study Period (Parts A and B)										Follow-up			Comments/Notes	
		CRU Inpatient Stay					Outpatient					Outpatient				
		-28 to -2	-1	1	2	3	4	5	6	8	15 ±1	29 ±3	43 ±3	ET		
Informed consent	X															
Medical history	X															
Physical examination	X															
Medical assessment			P	P	P		X	X	X	X	X	X	X	X	Medical review and symptom-directed physical examination, as appropriate.	
Height and weight	X		P		X				X	X	X	X	X	X	Height at screening only.	
Admit to CRU		X														
Discharge from CRU							X								At the investigator's discretion, participants may remain inpatient after Day 5.	
Outpatient visit to CRU								X	X	X	X	X	X	X		
Administer study drug			X	X	X										Refer to Section 6.1 for details	
AEs/concomitant medications	X	X	X	X	X	X	X	X	X	X	X	X	X	X		
ECG – single (h)	X		P, 1, 4, 12	P, 1, 4, 12	P, 1, 4, 12					X	X	X	X		ECGs must be recorded approximately within 30 minutes before collection of any blood samples (applicable for study visits).	
Vital signs: supine BP/PR (h)	X		P, 1, 4, 12	P, 1, 4, 12	P, 1, 4, 12	X	X	X	X	X	X	X	X			
Body temperature	X		P	P	P											
Clinical laboratory tests (fasted)	X		P				X		X	X	X	X	X		See Appendix 2 for details.	
Point-of-care safety glucose samples (glucose analyzer)			Days 1 – 4: Pre-meals (breakfast, lunch, and dinner) and before bedtime					X	X						Day 5: Fasted sample collected before breakfast.	

Study Activities	Scr n	Study Period (Parts A and B)									Follow-up			Comments/Notes
		CRU Inpatient Stay					Outpatient				Outpatient			
Days	-28 to -2	-1	1	2	3	4	5	6	8	15 ±1	29 ±3	43 ±3	ET	
LY3493269 PK sampling (h)		P, 0.5, 1, 1.5, 2, 2.5, 3, 4, 5, 6, 8, 9, 10, 12, 14	P, 1, 2, 3, 4, 8, 14	P, 0.5, 1, 1.5, 2, 2.5, 3, 4, 5, 6, 8, 9, 10, 12, 14	X	X	X	X	X	X	X	X	X	Days 15, 29, 43, and ET: Samples collected anytime during visit.
SNAC (Reference Formulation) or C10 (Test Formulations) PK sampling (h)		P, 0.5, 1, 1.5, 2, 2.5, 3, 4, 5, 6, 8, 9, 10, 12, 14	P, 1, 2, 3, 4, 8, 14	P, 0.5, 1, 1.5, 2, 2.5, 3, 4, 5, 6, 8, 9, 10, 12, 14	X	X								
Immunogenicity		P							X	X	X	X	X	Day 1: Samples are collected within 30 min of the predose PK samples.
Pharmacogenetic sample		X												Obtained any time on Day 1.

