#### Dosing in the fasted state

Participants will take each dose of LY3493269 on Days 1, 2, and 3 after the overnight fast. After each daily dose, participants must continue to fast for 2 hours or 30 mins, as described in [Table GZHI.6.1](#). Water ad libitum is allowed only until 1 hour before dosing and following the 2-hour postdose fast.

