#### Dosing in the fed state

For each participant, a high-fat, high-calorie breakfast meal shall be administered at the same time on each scheduled dosing day, to be consumed within 30 minutes.

Participants should be administered their assigned treatment 30 minutes after the start of the high-fat, high-calorie breakfast meal on each of the 3 dosing days. No food is allowed for at least 4 hours after the LY3493269 dose.

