**Table GZHI.6.1. Fasting or Fed Conditions and Water Consumption for Dosing**

Treatment	Formulation	Dosing Conditions a	Overnight Fast?	Water for Dosing (Approximate Volumes)	Dosing vs. Meal Timing
A1	Test 1	Fasted	Yes	120 mL	Postdose fast duration: 2 hours
A2	Test 2	Fasted	Yes	120 mL	Postdose fast duration: 2 hours
A3	Reference	Fasted	Yes	120 mL	Postdose fast duration: 2 hours
B1	“X”	B1(a) Fasted a	Yes	120 mL	Postdose fast duration: 2 hours
		B1(b) Fasted a	Yes	240 mL	Postdose fast duration: 2 hours
		B1(c) Fed a	Yes	240 mL	Dosing is scheduled 30 minutes after the start of the high-fat, high-calorie breakfast meal
B2	“Y”	B2(a) Fed	Yes	240 mL	Dosing is scheduled 30 minutes after the start of the high-fat, high-calorie breakfast meal
		B2(b) Fasted b	Yes	120 mL	Standardized breakfast meal provided 30 minutes postdosing

Abbreviations: vs = versus; X = test formulation 1, 2, or 3; Y = test formulation 1, 2, or 3 or reference formulation.

a Dosing conditions for Treatment B1 will be dependent on which Test Formulation is selected:

- If Test Formulation 3 (not tested previously) is selected as Formulation “X”, the dosing condition will be either B1(a), B1(b), or B1(c).
- If Test Formulation 1 or 2 is selected as Formulation “X”, the dosing condition will be either B1(b) or B1(c).

b This condition applies only to a scenario that further evaluates the Reference tablet formulation as Treatment B2.

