## **Changes from the Planned Study Design**

At the time of writing this SAP amendment, the Sponsor has decided not to proceed with Part B of the study. All further references to Part B are no longer applicable.

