#### **10.4.5 Clinical laboratory parameters**

All clinical chemistry and hematology data will be summarized by treatment and time point together with change from baseline, where baseline is defined as Day 1 predose, and listed. Urinalysis data will be listed. Additionally, clinical chemistry, hematology and urinalysis data outside the reference ranges will be listed and flagged on individual participant data listings.

Values recorded as  $< x$ ,  $\leq x$ ,  $> x$ , or  $\geq x$  will be displayed in the listings as recorded. For the calculation of summary statistics,  $< x$  and  $\leq x$  values will be set to  $0.5 \times x$ , whereas  $> x$  and  $\geq x$  values will be set to  $1.1 \times x$ .

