#### **10.4.6 Vital signs**

Vital signs data will be summarized by treatment and time point together with changes from baseline, where baseline is defined as the Day 1 predose assessment. Figures of mean vital signs and mean changes from baseline profiles will be presented by treatment.

Values for individual participants will be listed.

Change from baseline in supine blood pressure and pulse rate will be analyzed using a mixed model for repeated measures. The model will include baseline (Day 1 predose) as a covariate, treatment, timepoint and the treatment-by-timepoint interaction as fixed effects, and participant as a random effect. An unstructured covariance structure will be used to model the covariance

between a participant's multiple observations, with an alternative structure to be used if the model fails to converge. Follow-up data will not be included in the model.

One model including all treatments (A1, A2, A3, B1 and B2) will be used to present comparisons of each test formulation versus the reference formulation at each post-dose timepoint. The difference in least squares means, along with the 90% confidence interval, will be reported.

Example SAS code:

```
proc mixed data=xxxx;
  by param;
  class treat time subjid;
  model chg = base treat time treat*time / residual ddfm=kr2;
  repeated time / subject=subjid type=un;
  lsmeans treat*time / cl pdiff alpha=0.1;
  ods output lsmeans=lsm diff=diff;
run;
```

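### The point-of-care glucose baseline is tied to breakfast, not to the first dose, so in the fasted arms that remain a postdose or mixed baseline would comply with the rule

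*SAP*

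**What the plan says.** SAP 10.4.3 lists glucose and summarizes it by treatment with changes from baseline, "where baseline is defined as Day 1 pre-breakfast". Two neighbouring sections anchor baseline to the dose. For laboratory parameters (SAP 10.4.5) the wording is "where baseline is defined as Day 1 predose, and listed"; for vital signs (SAP 10.4.6) it is "where baseline is defined as the Day 1 predose assessment".

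The Schedule of Activities (Protocol 1.3) sets the point-of-care glucose samples on Days 1 to 4 by meals: "Pre-meals (breakfast, lunch, and dinner) and before bedtime". Single samples follow on Days 5 and 6. The Day 1 rows for ECG, vital signs, clinical laboratory tests and PK all carry the predose code P. The glucose row does not.

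On dosing, Protocol 6.1 (fasted state) says: "After each daily dose, participants must continue to fast for 2 hours or 30 mins". Table GZHI.6.1 gives A1, A2 and A3 the same entry: "Postdose fast duration: 2 hours". The 30-minute alternative belongs to a Part B condition. SAP Section 5 records that "the Sponsor has decided not to proceed with Part B of the study".

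**The concern.** A baseline for a drug-effect summary should be free of the drug. The pre-breakfast wording ensures that only where breakfast comes before the dose, as in the fed conditions, in which participants are "administered their assigned treatment 30 minutes after the start of the high-fat, high-calorie breakfast meal". Those conditions existed only in Part B. In the three remaining arms the order is reversed, and the definition no longer separates a predose sample from a postdose one.

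The compound acts on incretin receptors that potentiate insulin secretion (Protocol 2.2), so a fasting value taken after the dose cannot be presumed unexposed. If some or all baselines are postdose, any early glucose effect is partly subtracted out of every later change. If draw times differ between participants, the baseline is a mixture. If absorption timing differs between the capsules and the reference tablet, the arms could be affected unequally; that last step is inference, not something the documents show.

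**Working it through.** **Order of events on Day 1 in A1, A2 and A3**

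1. Overnight fast of at least 8 hours before the scheduled dose (Protocol 6.1), so no breakfast precedes dosing.
2. Morning dose, time 0.
3. Fast continues for 2 hours (Table GZHI.6.1), so breakfast is no earlier than 2 hours after the dose. This is inferred from the fasting rules; no clock time for breakfast is given.
4. A pre-breakfast sample may therefore be drawn at any point from before the dose until breakfast. No section requires it to be drawn before the dose.

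**Is there a separate predose point-of-care sample?**

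The Blood Sampling Summary (Protocol 10.2.1) gives 18 samples of 0.3 mL, 5.4 mL in total. From the schedule:

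- Days 1 to 4: 4 samples × 4 days = 16
- Day 5: 1
- Day 6: 1
- Total: 16 + 1 + 1 = 18, and 18 × 0.3 mL = 5.4 mL

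Both figures are reproduced exactly. Day 1 has one pre-breakfast sample and no additional predose one.

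**What depends on that one value**

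Post-baseline values per participant: 18 − 1 = 17, made up of:

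| Values | Count | Comparability with a fasting morning baseline |
|---|---|---|
| Pre-lunch, pre-dinner and bedtime, Days 1 to 4 | 3 × 4 = 12 | Change already reflects meals and time of day |
| Pre-breakfast, Days 2 and 3 | 2 | Morning, but dosing days with the same draw-time ambiguity |
| Pre-breakfast Day 4 and fasted Day 5 | 2 | Morning, no dose that day |
| Day 6 | 1 | No fasting condition stated |

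Check: 12 + 2 + 2 + 1 = 17. The more like-for-like morning comparisons number 2 + 2 = 4.

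Laboratory glucose has a Day 1 predose baseline (SAP 10.4.5) but is next scheduled on Day 5, then Days 8, 15, 29 and 43. No scheduled laboratory change falls on Days 1 to 4, so the point-of-care summary is the only glucose change shown for those days.

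**Direction of a possible effect**

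Let *f* be the fraction of an arm whose baseline was drawn after the dose, and *d* the mean lowering of glucose at that draw. Change is later value minus baseline, so the arm's mean change is shifted upward by *f* × *d*, which masks a fall. If *f* = 0 or *d* = 0 the shift is zero. The documents give neither quantity, so no figure in mg/dL is offered.

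**Does another rule settle it?**

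Protocol 9.3.1 makes Day 1 predose the default baseline but yields where another baseline is stated. SAP 10.4.3 states one, and SAP Section 3 says the SAP supersedes the protocol's statistical considerations. The default therefore does not secure a predose reading.

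**The case against.** The strongest reply is that this is a permitted possibility, not a shown error. In Part A a predose draw is also a pre-breakfast draw, and nothing directs staff to sample after dosing. The protocol default and the SAP sentence can be read as compatible. SAP Section 3 promises to identify substantial departures from the protocol, and SAP Section 12 lists only the cancellation of Part B. The missing P code is weak evidence: the glucose row is one merged entry for Days 1 to 4, Day 4 has no dose, and three of the four daily samples are not morning samples, so a predose label could not describe the whole entry. The SAP may simply be naming the sample by its scheduled label. The TFL shell document, which was not available for this review, might settle the matter.

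The effect may also be small. Participants are healthy and still fasting at that point, oral bioavailability is expected to be low (Protocol 4.2), and the same rule and the same 2-hour fast apply to all three randomized arms.

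Much of this stands. Predose may well have been intended, and no consequence has been demonstrated. It does not remove the ambiguity. Section 12 is not a complete list of departures: Protocol 9.3.3 has ECG parameters listed and summarized, SAP 10.4.7 does not present them, and Section 12 is silent on it. Equal treatment of the arms would not make a postdose value a valid baseline within an arm. A programmer following the sentence as written would use the pre-breakfast value whenever it was drawn.

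**Conclusion.** The concern holds as an ambiguity of minor severity. The definition admits a predose, postdose or mixed baseline in every arm that remains, and no other text available here resolves it. This rests on two readings: that the 2-hour postdose fast puts Day 1 breakfast after the dose in A1, A2 and A3, and that no instruction on draw time exists outside these documents.

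The reach is narrow. Only the descriptive point-of-care change from baseline is exposed. Observed glucose, individual listings, laboratory glucose change, hypoglycemia categories (which use absolute thresholds or clinical criteria), TEAEs and PK are unaffected. Glucose is not a study endpoint (SAP Section 4), and safety is evaluated descriptively (Protocol 9.1).

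**What to change.** In SAP 10.4.3, define the glucose baseline as the last point-of-care value before the first dose on Day 1, and use the pre-breakfast value only when it was drawn before that dose. Check this against the recorded dose times (Protocol 6.4) and the sample times where they exist.

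- If the samples were drawn after dosing, label them as a post-baseline time point and present observed values in place of change. There is no other planned predose point-of-care sample to substitute.
- Change from the Day 1 predose fasting laboratory glucose could be an optional supplementary summary, with a footnote that laboratory and analyzer methods differ.
- If sample times were not recorded, say so in a footnote. Protocol 8.4 requires actual sample times in its PK section; no section says so for point-of-care glucose, so the check may not be possible for every participant.

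The cost is one SAP sentence and, where needed, a footnote. No new data are required. If all samples prove to be predose, the results do not change and the definition becomes consistent with SAP 10.4.5 and 10.4.6.
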